#### DSMP Element 2: Data Storage and Confidentiality

This protocol will yield a mixture of electronic and paper data. All study records, database information containing subjects' data, and their identities will be kept confidential as required by HIPAA standards. All paper questionnaire response forms will be secured in a locked cabinet that has limited access. As electronic data from computerized behavioral tasks are collected at the McGuire VAMC, data will be transferred as needed using encrypted VA-issued thumb drive and stored on the secure RICVAMC virtual (U) drive with access limited to the PI and his designees, through use of a shared folder. Individual data files, such as spreadsheets for statistical analysis import will be individually password-protected. Finally, the RICVAMC virtual drive itself is also password- and PIV-card- protected.

Except when required by law, approved through a separate IRB protocol, or authorized by a HIPAA authorization or other approved mechanism (e.g., limited dataset, data use agreement, etc.), we will not identify subjects by name, social security number, address, telephone number, or any other personal identifier in study records outside the Richmond VAMC. For records disclosed outside RICVAMC, subjects will be assigned a unique protocol code number. The subject ID code file (i.e. linking each subject's protocol ID number/code his/her PII/PHI and medical record) will be maintained in an excel electronic file on the PI's VA-issued virtual drive. This code file will be a separate from any data-analysis file that would contain results of any testing, psychiatric interviews or questionnaires.

## **7. Recruitment:**

Recruitment: This project will recruit Veterans enrolled in the Substance Abuse Intensive Outpatient Program (IOP). The IOP includes five different groups over three days of the week for four weeks. Veterans are also randomly assigned to meet with a provider for four weekly individual sessions. Currently, Veterans either meet with one of two providers to complete the Mind Freedom Plan treatment, or they meet with a different provider to receive supportive, unstructured, therapy.

For the study, Veterans will be identified in their medical chart as being enrolled in IOP following the clinic intake and prior to beginning treatment. Research staff will contact Veterans face to face when they present to the SATP clinic to provide information about the study and explore if they are interested in participating. If they express interest, staff will schedule an appointment to meet with the potential participant to introduce the study, review and sign consent, and complete the baseline assessment self-report measure before they begin treatment.

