**1. Purpose and Objectives:**

This protocol does not include any administration of medication or other interventions. This protocol will record cognitive performance and decision-making behavior in Veterans who seek mental health services in the substance use disorder intensive outpatient program (IOP). The goal is to identify the neurobehavioral effects of a structured, brief cognitive-based psychotherapy currently being conducted in the IOP along with other supportive, unstructured, treatments. The benefit of this study will be to obtain a better understanding of neurobehavioral changes occurring from evidence-informed treatments.

Aim 1: To determine if measurable neurobehavioral function in the domains of problem solving, decision making, and motoric impulsivity is predictive of treatment success and adherence outcomes (e.g. Urinary Drug Screen/Breathalyzer Analysis results, appointment no shows, early drop out, recidivism).

Exploratory Aim: To determine if there are between group differences in neurobehavioral function as a result of treatment modality being received as standard of care in the substance use outpatient setting.

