### **3. Study Design:**

This protocol will recruit approximately 35 Veterans once they enroll in the McGuire VA Medical Center Substance Abuse Treatment Program (SATP) IOP to complete two sessions of questionnaires and neurobehavioral measures, lasting approximately 3 hours in total. Each subject will meet initially with research staff after their SATP intake (conducted as standard of care), but prior to initiating treatment for the first session. Subjects will then meet with research staff again approximately one month later following their completion (or potentially incompletion) of the treatment. Following this meeting, research staff will complete a targeted CPRS medical chart review to collect information on appointment no shows, early termination of services, and results of Urinary Drug Screen (UDS) and Breathalyzer collections, and results of the Beck Depression Scale and Quality of Life Inventory administered during the SATP intake. 90 days following this chart review, a second chart review will occur to collect the same information, if available, for the post-treatment time period, along with information about whether they have re-entered treatment.

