#### Data Analysis

The analytic plan includes conducting an independent-group t-test of each of the following continuous dependent variables, or chi-square for categorical dependent variables: 1)

proportion drug-free urines; 2) retention in program (Chi-Square); 3) Quality of life score on the QOLI; 4) Delay discounting constant k; 5) Stop signal reaction time (SSRT) on the stop-signal task; 7) Reaction time in the Emotional Go-NoGo task, 8) errors in the DKEFS Tower Test.

A repeated-measures design will be used to examine the within-subjects effects of the treatments on state depression and quality of life, as well as for a group X treatment interaction effect. Although we do not expect an intervention of this time scale of to alter trait impulsivity, we will also analyze within-subject changes in BIS11 scores as an exploratory analysis. Lastly, a between-group design comparing the MFP group vs. TAU group for substance use primary outcomes of symptomology and neurobehavioral measures for problem solving and impulsivity. Individual differences in PTSD and anxiety measures and other symptomatology will be included as covariates to account for confounding factors in the analyses.

c. Facilities and Resources

The consent procedures and behavioral testing of this protocol will take place in the new second-floor Mental Health services facility at RICVAMC. Written informed consent procedures and clinical interviewing will take place in private interview rooms of this new second-floor RICVAMC wing. Questionnaires and laboratory behavioral tasks will be administered at dedicated research task workstations installed in testing rooms.

d. Staff Qualifications

*[name].* will be the Principal Investigator of this protocol. [name] has a 5/8 VA appointment and a joint (faculty) appointment as Associate Professor of Psychiatry at Virginia Commonwealth University. He has extensive experience in the laboratory testing of impulse control and decision-making in addicted inpatients, outpatients, and at-risk human subjects. He is also known for his successful design and execution of protocols to examine the neurocircuitry of motivation and self-control in addicted and adolescent at-risk populations. He has over 50 peer-reviewed publications and book chapters, 48 of which are available in PUBMED.

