Risk/Benefit Assessment: This protocol is minimal risk. The investigative team contends that the benefits of this study in terms of generalizable neurobehavioral and psychiatric knowledge outweigh the risks to subjects.

Importance of knowledge to be expected: It is important to understand the effect of treatments being conducted in clinical settings here at McGuire VA Medical Center. This study has the opportunity to establish that a brief cognitive-based intervention is effective in treating patients with substance use disorders. Additionally, this study can expand our understanding of neurobehavioral effects of treatment on impulsivity and substance use outcomes.

Subject Compensation:

All subject compensation will come in the form of a direct deposit payment issued by the McGuire VAMC. The original grant funding source for this study was the Durham VA Mental Illness, Research, Education, and Clinical Center (MIRECC). These funds have been transferred to the McGuire VA Medical Center, and will be paid to participants directly from the VA. Subjects who consent to participate in the current study will be compensated \$20.00 for the first meeting (approximately 60-90 minutes), and \$30.00 for the second meeting (90 minutes).

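### Therapy and provider cannot be separated in the MFP-versus-supportive comparison, so the protocol's causal and effectiveness wording claims more than the design can give

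*Protocol*

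**What the plan says.** Section 7 (Recruitment) describes the clinic's current practice: "Veterans are also randomly assigned to meet with a provider for four weekly individual sessions". On the MFP side, "Veterans either meet with one of two providers to complete the Mind Freedom Plan treatment". Those assigned to the other therapy see someone else: "they meet with a different provider to receive supportive, unstructured, therapy". No provider is described as giving both therapies.

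Section 1 labels the treatment comparison exploratory but frames it as a search for "between group differences in neurobehavioral function as a result of treatment modality". Section 5, under the importance of the knowledge expected, states: "This study has the opportunity to establish that a brief cognitive-based intervention is effective".

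The Data Analysis text in Section 4 lists an "independent-group t-test of each of the following continuous dependent variables, or chi-square for categorical dependent variables", then a repeated-measures analysis, then a between-group comparison of MFP with TAU. The covariates named are PTSD, anxiety and other symptom measures; provider is not among them. The chart-review items in Sections 3 and 4 do not include the provider either. Section 3 gives the size: "This protocol will recruit approximately 35 Veterans".

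**The concern.** Random assignment here operates on the provider, and each provider brings one therapy. The MFP-minus-TAU contrast is therefore the effect of the therapy plus the difference between the MFP providers and the supportive provider in skill, alliance, attendance habits or anything else. With one provider on the supportive side, that arm holds no information on how much providers vary.

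What is at stake is the conclusion. Section 4 of the protocol notes no provider adjustment, and Section 2 places the exploratory aim within the VA's need for brief, efficacious therapies. A difference produced by one clinician could be read as evidence for MFP itself, because Sections 1 and 5 invite that reading.

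**Working it through.** **1. Who gives what (Section 7)**

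| Therapy | Providers | Shared with the other therapy |
|---|---|---|
| MFP | 2 | none described |
| Supportive (TAU) | 1 | none described |

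Provider is nested in therapy. Once a provider is known, the therapy is known, so a model with a separate fixed effect for each provider leaves no therapy effect to estimate. If providers are instead treated as the unit, there are 3 − 2 = 1 residual degrees of freedom. The two-sided 5% critical t is then 12.71, against 2.03 at 33 degrees of freedom for 35 individuals. In simulation, such a provider-level test has power of only about 0.10 to 0.14 at a standardised difference of 0.8 (ICC 0.10 down to 0, about 12 Veterans per provider). No model in a SAP could repair this.

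**2. The plan's own figure**

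The only size given is about 35 Veterans. No alpha, power, effect or SD is attached, so there is nothing to reproduce.

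**3. Illustration, only if inference is meant to go beyond these three providers**

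Assumptions, none of them in the protocol: alpha 0.05 two-sided; provider loads of 12 and 11 (MFP) versus 12 (TAU); unit outcome variance; provider ICC ρ from 0 to 0.10; an ordinary t-test of MFP versus TAU.

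True variance of the difference:

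V(ρ) = ρ·[(12² + 11²)/23² + 1] + (1 − ρ)·(1/23 + 1/12) = 1.501ρ + 0.1268(1 − ρ)

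The t-test takes the variance as 0.1268 (SE 0.356). With r = √[V(ρ)/0.1268], type I error ≈ 2·P(T₃₃ > 2.0345/r).

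| ρ | V(ρ) | r | 2.0345/r | Type I error |
|---|---|---|---|---|
| 0 | 0.1268 | 1.00 | 2.03 | 5.0% |
| 0.01 | 0.1406 | 1.05 | 1.93 | 6.2% |
| 0.02 | 0.1543 | 1.10 | 1.84 | 7.4% |
| 0.05 | 0.1955 | 1.24 | 1.64 | 11.1% |
| 0.10 | 0.2642 | 1.44 | 1.41 | 16.8% |

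Simulation of 100,000 null trials per row gives 6.3%, 7.5%, 11.7% and 18.1% for the last four rows. This is slightly higher because clustering also shrinks the t-test's own variance estimate. Loads of 9 and 9 versus 17 give similar simulated values: 6.3%, 7.8%, 12.2% and 19.6%.

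The provider part of the contrast has SD √(1.501ρ), which is 0.27 outcome SDs at ρ = 0.05 and 0.39 at ρ = 0.10. Recruiting more Veterans to the same providers does not reduce it.

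**The case against.** Several points on the other side stand.

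- **The study observes existing staffing.** Section 1 says the protocol administers no intervention, and Section 7 describes what the clinic does at present. The number of providers is not the investigator's design choice. This is why the remedy concerns the claim and the reporting.
- **Random assignment has value.** If it is truly random, it protects against patient selection. It does not protect against provider effects, because the provider is what is assigned.
- **The comparison is exploratory.** Aim 1, on predicting adherence, does not depend on it, and Section 5 speaks of an opportunity to establish effectiveness, not a certainty. That limits the damage; it does not make the sentence attainable.
- **The size of provider effects is unknown.** All Veterans also attend the same programme's five groups over three days a week; only the four weekly individual sessions are provider-specific, and several outcomes are computer-scored. The documents do not allow a judgement on whether an ICC of 0.10 is plausible.

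A reader might also infer that the planned t-tests simply have standard errors that are too small. The documents do not support that as a flat statement. The Data Analysis section does not say which groups the t-tests compare: some of the task hypotheses point to adherent versus non-adherent Veterans, and the MFP-versus-TAU comparison is named separately without a test. Even for MFP versus TAU, the inflation arises only if these providers stand for a wider population. Nor is the lack of an untreated group a defect, since the stated comparison is MFP against supportive therapy.

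**Conclusion.** The point holds as a limit of the design and of the stated conclusion. Therapy and provider effects are inseparable with two MFP providers and one different supportive provider, whatever the ICC and whatever a SAP might specify. The wording in Sections 1 and 5 therefore claims a property the design lacks. Should the phrase about a different provider loosely cover more than one person, provider would still be nested in therapy.

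The type I error figures are an illustration, conditional on the assumed ICC, loads and alpha and on inference beyond these providers. The issue is worth correcting before results are reported, but it touches an exploratory aim and leaves Aim 1 intact.

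**What to change.** 1. Add the individual-session provider to the chart-review items, and report outcomes by provider. Describe the gap between the two MFP providers without testing it; it carries one degree of freedom and is a poor gauge of provider variation.
2. Present MFP minus TAU as an exploratory estimate with CI for treatment as delivered by these providers, and state that therapy and provider cannot be separated.
3. Replace the Section 5 sentence with: *to explore whether outcomes differ between Veterans receiving MFP and supportive therapy*. In Section 1, replace the causal link to modality with wording on differences *between Veterans receiving each* treatment.
4. State which groups the listed t-tests and chi-square tests compare.
5. Only if inference beyond these providers is intended, add a separate sensitivity CI, labelled illustrative and widened for a stated range of assumed ICCs. It answers a different question from the estimate in item 2 and should be reported apart from it.

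Cost: one chart field, a short table, some rewording and a more modest claim. No additional Veterans or providers, and no change in care.

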#### Subject groups (inclusion and exclusion criteria):

##### *Inclusion criteria:*

- Enrollment in the Substance Abuse Treatment Program – Intensive Outpatient Program
- Currently meets criteria for an Alcohol or Substance Use Disorder per SUD clinic intake

*Exclusion criteria:*

- Unable to read and speak English
- Currently active-duty military
- Current engaged with legal involvement that is mandating the completion of the substance use program.

Collection of written informed consent:

The capacity to provide informed consent may be impaired in some patients, and we will not enroll decisionally-impaired individuals. Therefore, we will pay special attention to mental capacity and ability to provide informed consent. The determination of such capacity rests in a few key items:

- The subject should be able to understand the general procedures of the experiment and what is expected of him/her during participation.
- The subject should be able to understand the risks and benefits associated with the study.
- The subject should be able to understand that he/she can decline the study or withdraw from the study at any time after entering the study.

We will confirm that all participants understand the informed consent process by asking them to summarize the key points in their own words. The consent form will convey that confidentiality is limited in situations where the subject is assessed to be a threat in harming self or others. Subjects will be provided with a written copy of the consent form. The research staff will point out the contact numbers listed on the consent form for the PI [name] (for questions, comments, or concerns). Finally, as a safety precaution, each subject will be provided with a VA suicide hotline information card.

**8. Consultants:** none

**9. Curriculum Vitae:** Principal Investigator's CV is on file with other projects, but can be provided if requested.

